The headache questionnaire provided has been validated in English speaking populations only.

For guidance, refer to the following Partners policy:

Obtaining and Documenting Informed Consent of Subjects who do not Speak English

<http://healthcare.partners.org/phsirb/nonengco.htm>

RECRUITMENT PROCEDURES

Explain in detail the specific methodology that will be used to recruit subjects. Specifically address how, when, where and by whom subjects will be identified and approached about participation. Include any specific recruitment methods used to enhance recruitment of women and minorities.

Recruitment

Patient screening, recruitment and consent will occur at [name] clinic (MGH plastic surgery clinic) during a visit that determines their candidacy to undergo the surgery. As migraine prevalence is high in females we do not feel the need to enhance recruitment for women.

Patients are referred to the investigator or schedule an appointment independently for migraine surgery routinely. Subjects will be selected from among the patients that are referred to the investigator. A research nurse will initially explain participation in the study prior to the visit with the investigator. The patient will be given the consent forms and can take us much time as needed to consent for the study. The patient can also take the consent form home and call if interested. At the scheduled visit with the investigator he will reinforce that participation is voluntary and with their patients that participation is voluntary, that they do not have to participate, and the decision not to participate will not affect their care, now or in the future. The investigator can answer any questions the subject may have.

Subject Protection

Study subjects will not be employees of the study team.

Provide details of remuneration, when applicable. Even when subjects may derive medical benefit from participation, it is often the case that extra hospital visits, meals at the hospital, parking fees or other inconveniences will result in additional out-of-pocket expenses related to study participation. Investigators may wish to consider providing reimbursement for such expenses when funding is available

There is no subject remuneration.

For guidance, refer to the following Partners policies:

Recruitment of Research Subjects

<http://healthcare.partners.org/phsirb/recruit.htm>

Guidelines for Advertisements for Recruiting Subjects

<http://healthcare.partners.org/phsirb/advert.htm>

Remuneration for Research Subjects

<http://healthcare.partners.org/phsirb/remun.htm>

CONSENT PROCEDURES

Explain in detail how, when, where, and by whom consent is obtained, and the timing of consent (i.e., how long subjects will be given to consider participation). For most studies involving more than minimal risk and all studies involving investigational drugs/devices, a licensed physician investigator must obtain informed consent. When subjects are to be enrolled from among the investigators' own patients, describe how the potential for coercion will be avoided.

Speaking with and consenting participants will be conducted by [name]. Sufficient time will be provided for eligible participants to review the consent form and ask any questions. The PI or designated co-investigator will provide a full description of the consent form and ensure subjects' understanding of the study before the consent is signed. Subjects will receive the same treatment, whether or not they participate in the study.

NOTE: When subjects are unable to give consent due to age (minors) or impaired decision-making capacity, complete the forms for Research Involving Children as Subjects of Research and/or Research Involving Individuals with Impaired Decision-making Capacity, available on the New Submissions page on the PHRC website:

<http://healthcare.partners.org/phsirb/newapp.htm#Newapp>

For guidance, refer to the following Partners policy:

Informed Consent of Research Subjects

<http://healthcare.partners.org/phsirb/infcons.htm>

DATA AND SAFETY MONITORING

Describe the plan for monitoring the data to ensure the safety of subjects. The plan should include a brief description of (1) the safety and/or efficacy data that will be reviewed; (2) the planned frequency of review; and (3) who will be responsible for this review and for determining whether the research should be altered or stopped. Include a brief description of any stopping rules for the study, when appropriate. Depending upon the risk, size and complexity of the study, the investigator, an expert group, an independent Data and Safety Monitoring Board (DSMB) or others might be assigned primary responsibility for this monitoring activity.

NOTE: Regardless of data and safety monitoring plans by the sponsor or others, the principal investigator is ultimately responsible for protecting the rights, safety, and welfare of subjects under his/her care.

Describe the plan to be followed by the Principal Investigator/study staff for review of adverse events experienced by subjects under his/her care, and when applicable, for review of sponsor safety reports and DSMB reports. Describe the plan for reporting adverse events to the sponsor and the Partners' IRB and, when applicable, for submitting sponsor safety reports and DSMB reports to the Partners' IRBs. When the investigator is also the sponsor of the IND/IDE, include the plan for reporting of adverse events to the FDA and, when applicable, to investigators at other sites.

NOTE: In addition to the adverse event reporting requirements of the sponsor, the principal investigator must follow the Partners Human Research Committee guidelines for Adverse Event Reporting

The principal investigator ([name]) will be responsible for monitoring outcomes. No independent monitoring will occur. The principal investigator ([name]) will report adverse events to the IRB in accordance with the IRB adverse event reporting procedures.

The information collected during this study will be placed in a research folder, and not added to the patient's medical record unless deliberately requested by the patient. All research folders will be filed in locked cabinets, independent of clinical charts or any other medical record in electronic format. Any magnetic or electronic information will be saved in password-protected computers to which only study staff will have access.

Unanticipated problems involving risks to subjects or others including adverse events will be reported to the PHRC in accordance with PHRC unanticipated problems reporting guidelines.

MONITORING AND QUALITY ASSURANCE

Describe the plan to be followed by the principal investigator/study staff to monitor and assure the validity and integrity of the data and adherence to the IRB-approved protocol. Specify who will be responsible for monitoring, and the planned frequency of monitoring. For example, specify who will review the accuracy and completeness of case report form entries, source documents, and informed consent.

NOTE: Regardless of monitoring plans by the sponsor or others, the principal investigator is ultimately responsible for ensuring that the study is conducted at his/her investigative site in accordance with the IRB-approved protocol, and applicable regulations and requirements of the IRB.

The principal investigator ([name]) will be responsible for monitoring outcomes. No independent monitoring will occur. The principal investigator ([name]) will report adverse events to the IRB in accordance with the IRB adverse event reporting procedures.

The principal investigator is responsible for adherence to all IRB rules and guidelines and for the accuracy and completeness of all forms, entries, and informed consent.

For guidance, refer to the following Partners policies:

Data and Safety Monitoring Plans and Quality Assurance

<http://healthcare.partners.org/phsirb/datasafe.htm>

Adverse Event Reporting Guidelines

PRIVACY AND CONFIDENTIALITY

Describe methods used to protect the privacy of subjects and maintain confidentiality of data collected. This typically includes such practices as substituting codes for names and/or medical record numbers; removing face sheets or other identifiers from completed surveys/questionnaires; proper disposal of printed computer data; limited access to study data; use of password-protected computer databases; training for research staff on the importance of confidentiality of data, and storing research records in a secure location.

NOTE: Additional measures, such as obtaining a Certificate of Confidentiality, should be considered and are strongly encouraged when the research involves the collection of sensitive data, such as sexual, criminal or illegal behaviors.

All participants are given a participation number/ code at the time of enrollment. This code is kept on all data sheets instead of the patient's name. Subject information is only accessible by Partners authorized investigators and will not be shared with outside entities. The final results after statistical analysis will not be shared with any institution.

All clinical study records will be stored in a secure location in the office of [name], as all research activities involving patient data will take place at MGH.

SENDING SPECIMENS/DATA TO RESEARCH COLLABORATORS OUTSIDE PARTNERS

Specimens or data collected by Partners investigators will be sent to research collaborators outside Partners, indicate to whom specimens/data will be sent, what information will be sent, and whether the specimens/data will contain identifiers that could be used by the outside collaborators to link the specimens/data to individual subjects.

De-identified discarded tissue will be transferred to [name] lab at Beth Israel Deaconess Medical Center for processing and analysis. No personally identifiable data (including name, date of birth, age, and gender) will be shared between the clinical site (MGH) and the processing site (BIDMC).

Specifically address whether specimens/data will be stored at collaborating sites outside Partners for future use not described in the protocol. Include whether subjects can withdraw their specimens/data, and how they would do so. When appropriate, submit documentation of IRB approval from the recipient institution.

Specimens will only be used for this research study. Subjects can withdraw their specimens at any time.

RECEIVING SPECIMENS/DATA FROM RESEARCH COLLABORATORS OUTSIDE PARTNERS

When specimens or data collected by research collaborators outside Partners will be sent to Partners investigators, indicate from where the specimens/data will be obtained and whether the specimens/data will contain identifiers that could be used by Partners investigators to link the specimens/data to individual subjects. When appropriate, submit documentation of IRB approval and a copy of the IRB-approved consent form from the institution where the specimens/data were collected.

Collaborators will not collect specimens or data

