Those who agree to participate in the study, will be asked to fill out a 15min headache questionnaire that contains questions about their headaches. Subjects will also be asked to complete a headache diary 3 months prior to botox injections.

The headache diary will be filled out every day for 3 months prospectively prior to botox injection. Subjects will indicate whether they had migraines that day (check date box), what severity the migraines were (on a scale of 0-10), what the duration was (hours), what the location was, which other symptoms they experienced, which medications they took, how often they went to the ED, saw doctors or missed work and how much the total cost was. The total time spent every day filling out the diary should not exceed 5min.

Enrolled subjects will be injected with Botox on one side of the back of the head. The FDA-approved injection paradigm includes 7 muscles (Frontalis, Corrugator, Procerus, Occipitalis, temporalis, Trapezius, and the Cervical Paraspinal muscle group), 31 sites and 155 units divided as follows: Frontalis – 4 sites, 5 units in each; Corrugator – 2 sites, 5 units in each; Procerus – 1 site, 5 units; Occipitalis – 6 sites, 5 units at each; Temporalis – 8 sites, 5 units in each; Trapezius – 6 sites, 5 units at each; Cervical

Paraspinal – 4 sites, 5 units in each.

Of these muscles, sites and doses, patients will be injected (from a 100 Unit vial of OnabotulinumtoxinA reconstituted per product manufacturer label instructions) as follows:

- (A) 2 sites in the Occipitalis muscle (5 units each)
- (B) 4 sites in the Cervical Paraspinal muscle group (5 units each)
- (C) 2 sites in the Trapezius muscle (5 units each)

These injections will be given into one side only. This deviates from the standard of care, as Botox is usually injected on both sides if pain is experienced on both sides. The selection will be random based on subject number. Odd numbers will be injected on the right and even numbers on the left.

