Since the surgery, itself is unrelated to the proposed study, all patients (those who sign the informed consent and those who chose not take part in the study) are booked for the surgery. Usual waiting time is 3-6 month. Those who signed the informed consent will be booked for another visit to [name] clinic 30 days prior to their planned surgery. In this visit, they will be injected with 40 units of Botox in one side of their head/neck as detailed below.

During surgery, calvarial periosteum, pericranial muscles and fascia surrounding nerves that are routinely removed and discarded, will be collected by [name], stored in in RNAlater Solution, Ambion, CA, de-identified, frozen, and shipped overnight to [name] lab at BIDMC, where each sample will be recorded, verified, prepared for processing, and analyzed for targeted transcriptome and epigenome involved in inflammatory and immune responses.

The current standard of care for screening for migraine surgery includes injection of Botox to identify nerve triggers. In the occipital region, botox is either injected unilaterally or bilaterally depending on where pain occurs. When pain occurs bilaterally, Botox is injected on both sides. Subjects included in this study have bilateral occipital pain and would therefore as part of routine standard care be injected on both sides. As per this protocol, subjects will only be injected on one side. The risks of unilateral injection of botox (in addition to the risk of Botox in general outlined by the FDA) include continued pain on the uninjected side and/or injected side and one- sided muscle weakness, one- sided bruising, one sided infection on the injected side. . More generally, botox injections may cause the formation of anti-botox antibodies, which may decrease the effectiveness of botox treatment in other areas.

Subjects will be informed that they have the option to be injected with Botox on the uninjected side if any unwanted symptoms are experienced on the uninjected side. The cost of injection on the other side will be covered by the study funds.

A separate IRB protocol has already been approved for the use of discarded tissues, therefore this is also standard procedure.

Describe how risks to subjects are minimized, for example, by using procedures which are consistent with sound research design and which do not unnecessarily expose subjects to risk or by using procedures already being performed on the subject for diagnostic or treatment purposes.

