All proposed procedures are part of standard care for chronic migraine patients except for unilateral injection of Botox for which the risks are explained above.

Describe explicitly the methods for ensuring the safety of subjects. Provide objective criteria for removing a subject from the study, for example, objective criteria for worsening disease/lack of improvement and/or unacceptable adverse events. The inclusion of objective drop criteria is especially important in studies designed with placebo control groups.

From the time of informed consent and for 3 months following injection, all self-reported adverse events will be reviewed by the study physician at each patient contact (patients are followed every 4 weeks after botox injection and one week, one month, three months, one year and after that yearly after surgery). All serious adverse events will be reported to the IRB and designated

safety monitor within 24 hours of awareness of the event. All unanticipated problems involving risks to subjects or others including adverse events will be presorted to the PHRC in accordance with PHRC unanticipated problems including adverse events reporting guidelines.

Patients will not be included in the study if they are deemed poor candidates for surgery (screening occurs independent of this study).

Only subjects who have been selected as a surgical candidate for sensory nerve decompression of chronic headache would have their tissue tested. The taking of the periosteal sample would add no additional risk to the operation, as we are obtaining tissue discarded during surgery.

Botox therapy is currently approved by the FDA for preventive treatment of migraines. Possible side effects of Botox therapy include bruising, pain during injection, twitching, itching, and numbness.

Overall, we believe the risks of this study are sufficiently low and that the benefits of information to be gained and the potential benefit of improved migraine treatment outweigh the risks in this study.

Patients can elect to withdraw from the study at any time.

FORESEEABLE RISKS AND DISCOMFORTS

Provide a brief description of any foreseeable risks and discomforts to subjects. Include those related to drugs/devices/procedures being studied and/or administered/Performed solely for research purposes. In addition, include psychosocial risks, and risks related to privacy and confidentiality. When applicable, describe risks to a developing fetus or nursing infant.

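### The Consent Procedures section says treatment is the same with or without participation, but the protocol makes the Botox injection and a medication restriction depend on participation

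*Combined protocol and SAP*

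**What the plan says.** In the Protocol Summary, the Consent Procedures section describes who obtains consent, allows enough time for review, and ends: "Subjects will receive the same treatment, whether or not they participate in the study".

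Elsewhere the file describes the injection differently.

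- Main protocol section 3.A, and the standard-of-care answer in the Protocol Summary: "Subjects included in this study have bilateral occipital pain and would therefore as part of routine standard care be injected on both sides". Both continue: "As per this protocol, subjects will only be injected on one side".
- Main protocol section 3.A (Clinical Site Study Procedures), and Research Design and Methods in the Protocol Summary, on giving the injections to one side: "This deviates from the standard of care, as Botox is usually injected on both sides if pain is experienced on both sides".
- Protocol Summary, answer on how risks are minimised: "All proposed procedures are part of standard care for chronic migraine patients except for unilateral injection of Botox".
- Main protocol section 3.A and the Protocol Summary, on the risks of one-sided injection: "continued pain on the uninjected side and/or injected side", among others.

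The inclusion criteria (main protocol section 3.C and the Protocol Summary) also require participants to agree to avoid excluded medications from 14 days before surgery.

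Both parts of the file say that subjects will be told of an option, paid for by the study, to have the other side injected if unwanted symptoms occur there.

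**The concern.** A statement that treatment does not depend on participation is a factual claim about the design. Here the design works by making treatment depend on participation: one side is left uninjected so that each patient supplies an untreated comparison. The sentence therefore denies the feature on which the study rests.

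What is at stake is participant protection. The difference from usual care, and the listed risk of continued pain, are what a candidate has to weigh. The sentence stands in the section an ethics committee reads to judge how consent is obtained. The Protocol Summary also makes the principal investigator responsible for the accuracy of forms and informed consent, so an inaccurate statement in this section should not remain.

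**Working it through.** There is no figure to reproduce and no formula applies. The check is a comparison of the current text on what changes, and what does not change, with participation.

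| Item | Described without participation | Described with participation | Same? |
|---|---|---|---|
| Decision to operate (3.A, 3.C; Summary, Research Design and Methods) | Independent of any study | Independent of any study | Yes |
| Booking for surgery (3.A; Summary, standard-of-care answer) | Booked | Booked | Yes |
| Botox injection (3.A; Summary) | Routine care for bilateral pain is both sides | One side by default, at a visit 30 days before surgery booked for those who consent | No |
| Medication (3.C; Summary, inclusion criteria) | No study restriction | Excluded medications avoided from 14 days before surgery | No |

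Step 1. The sentence says treatment is the same in both columns. It holds for the first two rows and fails for the last two.

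Step 2. Could the injection row be rescued by what a patient who declines would actually receive? The documents do not fully settle this. They describe injection on both sides as part of screening for surgery, and they also say that those who qualify have already had Botox at least twice. A patient who declines might therefore get a further bilateral injection, or none before surgery. One-sided injection differs from either, so the contradiction does not depend on the answer.

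Step 3. Could the optional second injection make the two equal? No. It is conditional on unwanted symptoms on the uninjected side. The default remains one side.

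Step 4. Is the conflict an artefact of the file? No. Every statement compared is current text; none comes from a change log or a redacted passage. The list of excluded medications is in an appendix not in the file reviewed, so how much that restriction would alter any one patient's care cannot be judged. That it applies only to participants is clear.

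**The case against.** The strongest defence is that the sentence answers a form prompt that ends by asking how coercion will be avoided. Read that way, it means that nobody is penalised for declining. The recruitment text (main protocol section 6 and Recruitment Procedures in the Protocol Summary) says that correctly: declining will not affect the patient's care. The same Protocol Summary discloses the one-sided injection, its risk and its status as an exception to standard care, so a committee reading the whole document would not be misled about the design. This is a fair account of the likely intention. It does not make the sentence true, because the sentence is broader than a promise of no penalty and the recruitment text is a different statement.

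Three stronger readings are tempting and are not supported.

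- A reader might infer that patients are told something false. The sentence is in a procedure written for the ethics committee. The consent form is not in the file and may be accurate. The sentence just before it promises a full description of the consent form, and subjects are to be told of the second-side option.
- A reader might infer that the misstatement will cause withdrawals or second-side injections, and so cost own-control pairs. The documents give no rate for either and no link to this sentence. The second-side option exists however the sentence is worded. The plan also allows up to 65 recruits against the 50 in the power statement.
- A reader might infer that the one-sided injection is the only change in care. The summary's list of exceptions suggests so, but the medication restriction is another.

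**Conclusion.** The point holds as a contradiction in the text. The Consent Procedures sentence is wrong as written, because both the Botox injection and a medication restriction depend on participation. It applies to every participant, up to 65. It has no numerical effect on power, sample size or analysis, and none is claimed. Its weight comes from where the sentence stands and from the listed risk of continued pain, and one short change corrects it.

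The conclusion rests on the documents' own description of routine care for these patients. It assumes nothing about the content of the consent form, and it takes no view on which injection practice is right.

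**What to change.** Reconcile the Consent Procedures sentence with main protocol sections 3.A and 3.C and with the design, standard-of-care and risk answers in the Protocol Summary.

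1. Limit the claim of sameness to what the documents support: the decision to operate, the booking for surgery, and that declining carries no penalty in later care.
2. State in the same place that the Botox injection and the medication restriction before surgery differ with participation, and point to the listed risk of continued pain.
3. If the opposite-side injection is mentioned there, describe it only on the documents' own condition, which is unwanted symptoms on the uninjected side.
4. Check that the consent form does not repeat the sentence.

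The cost is a one-sentence amendment and one document check. The possible downside is slightly slower recruitment.
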